8.3 General Analytic Strategy

The primary evaluation of EQ-5D at four-weeks will be conducted using an ITT analysis, where patients' data are analyzed according to the patients' randomized treatment assignment. Using this analytic approach in a non-inferiority study design comparing antibiotics treatment to appendectomy, we aim to test whether the global EQ-5D scores are not different by more than a margin of 5% (M = 5%). The margin (5%) was selected because it is within the meaningful clinical important difference (MCID) threshold of the EQ-5D, which is 5-10%.

1. Primary Analysis, Aim 1 - Patient-reported QoL, as measured by the EQ-5D at fourweeks, will be assessed using a linear regression model that adjusts for an indicator of randomized treatment group assignment and for all factors used to stratify randomization (e.g., practice site). As recommended by the United States Food and Drug Administration guidelines on clinical trial design. 26 the estimated treatment effect and 97.5% one-sided confidence interval (CI) will be compared to the non-inferiority margin (M = -5%). ²⁷⁻²⁹ We will conclude that antibiotics are non-inferior to appendectomy when the entire 97.5% one-sided confidence interval is greater than M (Figure 1, example trial conclusion A). This is equivalent to a one-sided (α=0.025) test of the null hypothesis H_0 : $\Delta < -5\%$, where Δ represents the difference in mean EQ-5D at four-weeks comparing the antibiotics treatment strategy to the appendectomy treatment strategy. If the null hypothesis of H_0 : $\Delta < -5\%$ is rejected at the final evaluation, we will conduct a test of superiority to determine the level of statistical evidence supporting an alternative hypothesis H_A : $\Delta > 0\%$ (Figure 1, example trial conclusion B). For Sub Aim 1, we will similarly evaluate non-inferiority on patient-reported QoL among the cohort without appendicolith.

[figure not shown]

Figure 1. Example Trial Conclusions in a Non-inferiority Trial.

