8.5 Sample Size and Statistical Power

Prior studies suggest that non-clinical outcomes (e.g., loss of time from work and pain scores) were similar between groups, but did not evaluate a global QoL measure. The EQ-5D QoL

index ranges from 0 (worst QoL) to 1 (highest QoL), where anchor-based methods have shown that the MCID ranges 5%-10%. Based on data from a prior study of appendectomy with EQ-5D scores at 12 weeks, we estimate that the mean EQ-5D for appendectomy patients will be 0.90 with a standard deviation of 0.12. In order to assess QoL differences between interventions, we will recruit a total of 1552 patients assuming a 90% follow-up at four-weeks. This gives the study high power (>99%) to rule out EQ-5D differences between-groups as small as 5% (e.g., if we observe treatment differences of 0 to 2%) and 80% power if we observe a treatment difference of 3% (Table 5, below).

Previous Washington State evaluations of patients undergoing appendectomy (Table 1). identified that 2-3% of the population is African American, 10-12% Hispanic, 10-15% are Medicaid beneficiaries, and 10% will be above 64 years of age. Recruiting 1552 total patients will allow for a subgroup evaluation based on older age and Medicaid beneficiary status. Assuming 50% recruitment of these populations we anticipate including ~500 Medicaid beneficiaries and ~450 patients ≥65 years. As demonstrated in Table 5, this study also has adequate power (>80%) to rule out differences of 5% for observed treatment effect of Δ =0% within subgroups as small as n=250 patients, or treatment differences of Δ =-1% within subgroups of at least n=400. For this reason, we expect the study will be able to assess these two subgroups. All other subgroup evaluations will be post hoc and used for hypothesis development only.

Table 5. Statistical Power to Declare Non-inferiority on Patient-reported QoL, Overall and by

Subgroup (Non-inferiority Margin, M = -5%, one-sided α =0.025).

Treatment Difference A	Overall		Subgroups	
Treatment Difference, Δ	N=1552	N=250	N=400	N=500
-3%	82.6%	-	-	-
-2%	99.4%	-	57.1%	67.9%
-1%	100%	62.4%	83.8%	91.4%
0%	100%	83.0%	96.4%	98.8%

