General Analytic Strategy: The primary evaluation of EQ-5Dat 4 weeks will be conducted using an intention-to-treat (ITT) analysis, where patient data areanalyzed according to the patient's randomized treatment assignment. Using this analytic approach in a non-inferiority study design comparing antibiotics-first treatment to appendectomy, we aim to test whether the global EQ-5D scores are not different by more than a margin of 5% (M = 5%). The margin (5%) was selected because it is within the meaningful clinical

important difference (MCID) threshold of the EQ-5D, which is 5-10%¹⁻³.

Primary Analysis. Aim 1: Patient-reported QoL, as measured by the EQ-5D at 4 weeks, will be assessed using a linear regression model that adjusts for an indicator of randomized treatment group assignment and for all factors used to stratify randomization (i.e., practice site and appendicolith). As recommended by the United States Food and Drug Administration guidelines on clinical trial design⁴, the estimated treatment effect and 97.5% one-sided confidence interval (CI) will be compared to the non-inferiority margin (M = -5%)⁵⁻⁷. We will conclude that antibiotics are non-inferior to appendectomy when the entire 97.5% one-sided confidence interval is greater than M, as in example scenario A (Figure 1). This is equivalent to a one-sided (alpha=0.025) test of the null hypothesis H₀: $\Delta \leq -5\%$, where Δ represents the difference in mean EQ-5D at 4-weeks comparing antibiotics-first to appendectomy-first. If the null hypothesis of H₀: $\Delta \leq -5\%$ is rejected at Figure 1. Example trial conclusions in a non-inferiority trial.

the final evaluation, we will then conduct a test of superiority to determine the level of statistical evidence supporting an alternative hypothesis $H_A: \Delta > 0\%$ (i.e., scenario B of Figure 1). For Sub Aim 1, we will similarly evaluate non-inferiority on patient-reported QoL among the cohort *with and without* appendicolith. Patients whose randomization was

performed for the incorrect appendicolith group (e.g., research coordinator selected the wrong button during randomization) will be assigned to the group representing their true status.

Aim 1 Secondary Analyses: Secondary analyses of the primary outcome measures will include examining the entire trajectory of EQ-5D QoL measurements for each patient using statistical methods for longitudinal data such as linear mixed effects models or generalized estimating equations (GEE).⁸

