Aim 2 Analysis Plan: Clinical endpoints (see Outcome Measures above) will also be compared between ITT groups using regression models appropriate to each endpoint (e.g., linear, logistic, Poisson, or Cox proportional hazards regression models), along with a similar non-inferiority framework with margins based on MCIDs when available. **For Sub Aim 2**, we will similarly evaluate clinical endpoints among the cohort with and without appendicolith. The goal is to estimate treatment effects within each subgroup based on appendicolith.

Exploratory Aim B Analysis Plan: One assumption is that patients included in the randomized trial are sufficiently similar to those from the general population of patients with appendicitis. Using simple univariate descriptive and comparative statistics (e.g., t-tests, Chi-squared tests), we will compare randomized patients to those in the parallel observational cohort to identify selection bias. We will also compare the primary outcome measures between randomized and non-randomized patients by examining the entire trajectory of EQ-5D QoL measurements using linear mixed effects models or GEE for longitudinal data, providing an assessment of differences in the rate of change of quality of life. We will adjust for patient- or provider-level characteristics found to be differentially represented in RCT. Using methods similar to those described in the plan for Aim 1 Secondary Analyses, we will adjust for treatment received to fully assess whether patients who participate in the RCT have a different outcome trajectory than patients in the observational cohort.

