Missing Data: We will conduct a missing data analysis to describe andcharacterize enrolled participants who do not provide data due to attrition. Specifically, we use 10-fold multiple imputation to assess the robustness of the results when missing data are imputed. In addition, as described by Molenberghs and Kenward (2007), we will also use inverse probability weighting in secondary analysis within each longitudinal regression model to inflate the weights of cases that are under-represented in the analysis due to selective attrition and/or non-participation. We will assess the sensitivity of inferences made from missing data first by using the two previously described methods for dealing with missing data and second, by imputing missing data under both pessimistic and optimistic scenarios to provide bounds on the statistical uncertainty. The characteristics of non-responders will be summarized in our final report and we will present the sensitivity of the estimated treatment effect due to alternative missing data methods.

Additional Exploratory Subgroups: We will also evaluate outcomes in selection subgroups including advanced age, sex, comorbid conditions and insurance status. For these analyses we will focus on evaluation of statistical interactions with treatment to assess treatment effect heterogeneity.

Statistical Analysis Plan References

1. Rabin R, de Charro F. EQ-5D: a measure of health status from the EuroQol Group. Ann Med. 2001 Jul;33(5):337-43. PMID:11491192

4. International Conference on Harmonisation E9 Expert Working Group. (1999). ICH harmonised tripartite guideline: statistical principles for clinical trials. Stat Med 18(15):1905-42. PMID:10532877

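### Non-inferiority on EQ-5D is judged separately with and without appendicolith, but no treatment-by-appendicolith interaction is planned, so equal effects can be read as non-inferiority only without appendicolith

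*SAP*

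**What the plan says.** - **Final SAP, Primary Analysis, Aim 1.** The primary model is a linear regression of four-week EQ-5D on randomised arm, site and appendicolith. The decision rule compares a 97.5% one-sided interval with the margin: "This is equivalent to a one-sided (alpha=0.025) test of the null hypothesis". For the strata it adds "For Sub Aim 1, we will similarly evaluate non-inferiority on patient-reported QoL among the cohort" with and without appendicolith. That is the same rule applied twice more. No interaction term, order or alpha allocation is given for these tests. The only stated sequence is non-inferiority, then superiority, in the overall analysis.
- **Final SAP, Additional Exploratory Subgroups.** For advanced age, sex, comorbid conditions and insurance status, "we will focus on evaluation of statistical interactions with treatment to assess treatment effect heterogeneity". Appendicolith is not on that list.
- **Final SAP, Aim 2 Analysis Plan.** For clinical endpoints, "The goal is to estimate treatment effects within each subgroup based on appendicolith".
- **Protocol 8.3.** Sub Aim 1 covers one stratum only: "we will similarly evaluate non-inferiority on patient-reported QoL among the cohort without appendicolith".
- **Status of the subgroup.** Protocol 2.1 describes the appendicolith evaluation as pre-specified. Protocol 8.5 names older age and Medicaid as the subgroups that it can assess, and calls all other subgroup evaluations post hoc and for hypothesis development.

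**The concern.** Appendicolith is the one clinical factor used to stratify randomisation, yet its plan for effect heterogeneity is weaker than the plan for the exploratory subgroups. Two pass/fail verdicts do not compare two effects. If the appendicolith stratum is the smaller one, its interval is wider, and it can miss the margin while the larger stratum clears it with exactly the same true difference. A reader shown one pass and one fail for the trial's main subgroup may take this as evidence that antibiotics suit only patients without an appendicolith. The plan does not commit to reporting the direct comparison that would test that reading.

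**Working it through.** **Inputs.** Protocol 8.5: "we will recruit a total of 1552 patients assuming a 90% follow-up at four-weeks" and "the mean EQ-5D for appendectomy patients will be 0.90 with a standard deviation of 0.12". One-sided alpha is 0.025. The margin is 5%, on a scale that is not stated, so I use 0.05 (absolute) and 0.045 (5% of 0.90). The appendicolith share is not in the documents. I assume 25%, with a range of 20-35%.

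**The plan's own figures.**
- Sample size per arm is 2 × 0.12² × (1.960 + 0.842)² / (margin − |Δ|)². With margin 0.045 and Δ = -0.027 (both relative to 0.90) this gives 698 per arm, and 1396 / 0.9 = 1552 after rounding up. That matches. With 0.05 and -0.03 the total is 1258.
- Table 5 does not reproduce exactly on either scale. For N=400 at -2% it states 57.1%; I get 66.0% (absolute) and 56.9% (margin and difference both relative). For N=1552 at -3% it states 82.6%, against 87.6% and 80.0%. I therefore give results for both margins.

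**Stratum power.** With N randomised in a stratum and 1:1 allocation, SE = 0.24 / √(0.9N). Power = 1 − Φ(1.96 − (M + Δ)/SE). At a 25% share:
- With appendicolith, N = 388 and SE = 0.01284.
- Without appendicolith, N = 1164 and SE = 0.00742.

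**Discordance when the true effect is the same in both strata.** The strata are independent, so the chance of non-inferior without, not shown with, is power(without) × [1 − power(with)].

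| True Δ in both strata | M = 0.05: power with / without | Discordant | M = 0.045: power with / without | Discordant |
|---|---|---|---|---|
| 0 | 97.3% / 100% | 2.7% | 93.9% / 100% | 6.1% |
| -0.01 | 87.6% / 100% | 12.4% | 77.8% / 99.7% | 22% |
| -0.02 | 64.6% / 98.2% | 34.7% | 49.5% / 92.1% | 46.5% |

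If Δ as well as the margin is read as relative to 0.90, the upper figures at -1% and -2% become about 20% and 42%.

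**Sensitivity to the share.** With M = 0.05 and Δ = -0.02, discordance is 44% at a 20% share and 20% at 35%. With M = 0.05 and Δ = 0, a 35% share gives 0.4%.

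**Cross-check on Table 5.** Its N=400 column corresponds to a share of 400/1552 = 26%. One minus the stated power (96.4%, 83.8%, 57.1%), times the power of the other 1152 patients (about 100%, 100% and 98%), gives 3.6%, 16% and about 42% at 0, -1% and -2%.

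**What an interaction would do.** Its SE is √(0.01284² + 0.00742²) = 0.0148. The 95% half-width is 1.96 × 0.0148 = 0.029, and the difference detectable with 80% power is 2.80 × 0.0148 = 0.042. With a 25% share and M = 0.05, suppose a claim of difference needs both the discordant verdict and a significant interaction (two-sided 0.05). By simulation, its chance under equal effects falls from 34.7% to 2.5% at -2%, from 12.4% to 2.4% at -1%, and from 2.7% to 1.4% at zero.

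**Multiplicity (a separate question).** If every true difference sits at the margin, the two stratum tests alone give 1 − 0.975² = 4.9% for at least one false claim. Adding the overall test gives about 5.7% by simulation at a 25% share.

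**The case against.** - **The contrast can be recovered.** Because Sub Aim 1 follows the primary analysis, each stratum should have an estimate and an interval. With one binary factor, the difference and its SE follow from those. This stands, so it would be wrong to say that nothing planned could expose a sample-size artefact. What is missing is a commitment to report the contrast and to base any claim on it.
- **No misreading is planned.** Nowhere do the documents say that the two verdicts will be contrasted, and the stated goal for Sub Aim 2 is estimation within subgroups. This also stands: the risk is left open, not written in. For Sub Aim 1, however, the wording is evaluation of non-inferiority, which is a verdict.
- **The frequency depends on unknowns.** A reader might infer that equal effects will often give split verdicts. The documents do not support that. Table 5 covers differences from 0 to -3%, and near zero the chance is small at a share of 25% or more. The share itself is assumed.
- **The interaction is imprecise.** A detectable difference of about 0.04 is nearly the whole margin. This is true, but the term is there to restrain an unsupported claim; it would rarely establish real heterogeneity.
- **Subgroups other than age and Medicaid are post hoc under protocol 8.5.** If that governs, the multiplicity point falls away. It conflicts with protocol 2.1, so the status is unsettled.

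**Conclusion.** The gap is real and cheap to close. The final SAP gives two stratum verdicts and no planned comparison of them, so identical effects can look like a benefit confined to patients without an appendicolith. The size is conditional. With a 25% share, SD 0.12 and 90% follow-up, it is about 3-6% at no difference, 12-22% at -1% and 35-46% at -2%, for margins of 0.05 to 0.045.

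A reader might also blame the missing test order for the split verdicts. It does not cause them: a fixed order would still allow a pass without and a fail with appendicolith. Order bears only on the error rate over several tests, and only if Sub Aim 1 is confirmatory, which the documents leave in conflict. The overall ITT conclusion on EQ-5D is untouched.

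**What to change.** 1. Keep the main-effects model for the overall non-inferiority test. As a supporting analysis of EQ-5D, and in the Aim 2 models, add a treatment-by-appendicolith term.
2. Report both stratum estimates and the interaction, each with a 95% CI. Say that the effect differs by appendicolith only if the interaction interval supports it, and say in advance that a non-significant interaction is not evidence of equal effects.
3. Reconcile the status of Sub Aim 1 across protocol 2.1, 8.3 and 8.5 and the final SAP, including which strata it covers. If it is confirmatory, fix an order, for example overall, then without, then with appendicolith. If not, label the stratum results as supportive estimates.

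The cost is one model term and a few sentences, with no new patients or data. The interaction will be imprecise (SE about 0.015). Under a fixed order, a stratum claim is lost whenever an earlier test fails.

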Inspired by the antibiotics-only approach results between 1956 and 2015, and with advances in radiologic imaging to diagnose and stage the progression of disease, there were six randomized trials comparing antibiotics to appendectomy among patients with AUA. These trials, all performed in Europe. 6-11 found that nearly 3 out of 4 patients in the antibiotics treatment group avoided surgery in the first year after diagnosis. A meta-analysis of five of these studies (the most recent published in 2015) found that antibiotic treatment was associated with a 46% reduction in complications and less pain and disability than routine appendectomy. 12 No participant deaths occurred in the trials, and the rates of perforation were lower among those in the antibiotic treatment group. However, existing trials suffer from important limitations. These include small sample sizes leading to indeterminate results, lack of imaging leading to potential inclusion of patients with complicated appendicitis and potentially without appendicitis at all, inexact and treatment dependent outcome definitions (rate of appendectomy) and operation/reoperation criteria, arbitrarily prolonged hospitalization, limited use of laparoscopic techniques. inadequate antibiotic regimen activity, and short-term follow-up (no studies followed patients beyond one year). Furthermore, none of these trials included keeping a record of the patient's experience with treatment in a standardized fashion. Perhaps as a result of these evidence gaps, nearly all United States (U.S.) patients with appendicitis (97.5% according to a recent California [CA]-based administrative database analysis¹³ and similar findings in Washington [WA] [personal communication [name]]) undergo appendectomy. Conversely, in Europe where the trials originated, it now appears that 1 in 5 patients with AUA are being offered the antibiotics approach.

It remains to be determined whether patient experience with the antibiotics strategy (performing appendectomy only when the patient gets worse on antibiotics or has a recurrence of disease) is "just as good as" appendectomy. This comparison should consider the overall impact of the treatment on their health, well-being, quality of life (QoL), healthcare burden, and all clinical endpoints (e.g., resolution of symptoms, need for eventual appendectomy, complications). It also remains to be determined what patient and clinical factors are associated with worse outcomes.

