4.2 Inclusion Criteria

- 1. Adult ≥18 years;
- First clinical diagnosis of AUA established by clinical care team, supported by any of the following usual care radiological tests (CT, US, and/or MRI). AUA is defined by the usual signs, symptoms, and imaging finding of appendicitis without:
 - a. Diffuse peritonitis on clinical exam (i.e., rigid abdomen / four quadrant peritonitis);
 - b. Radiologic findings of:
 - i. Free air;
 - ii. Walled off fluid collection concerning for an abscess;
 - iii. Significant amounts of intra-abdominal fluid throughout abdomen (i.e., more than trace fluid); or
 - iv. Extent of inflammation or adjacent organ involvement on radiologic imaging such that urgent appendectomy is relatively contraindicated or not intended.
- 3. Ability to provide written informed consent in English or Spanish.

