5.3 Medical Record Review

Time points

Patients consenting to the study will have their EMR reviewed at (1) pre-determined time points and (2) ad-hoc time points if triggered by a survey response. RCs will conduct an EMR review to assess the following:

- Complications for patients using the National Surgical Quality Improvement Program (NSQIP) definitions and protocol as well as those complications related to antibiotic use; and
- 2. Healthcare utilization events since index hospital discharge. Details of all healthcare utilization events related to appendicitis will include the following information:
 - a. Length of stay;
 - b. Use and results of repeat imaging; and
 - c. Surgery type, if applicable.

The 3 cohorts will undergo pre-determined review at the following time points:

The e concre will andergo pre determined review at the following time points.							
	Randomized & Observational	EMR Only Cohort					
	Cohorts						
Index Visit	X	X					
Week 1	X						
Week 2	X						
Week 4	X	X					
Year 1	X						
Year 2	X	X					

As needed, ad-hoc chart review will be conducted if a patient reports an adverse event and further documentation is needed.

When possible, participants will continue to have their EMR reviewed at Year 3, Year 4, and Year 5.

Data Collection

Data is collected using the following forms:

Form	Description
Form Information	Captures information about when the form was filled out (time point), and by whom
ED Visit Form	Captures information about the hospital visit (demographics, admit/discharge times, symptoms)
Imaging Form	If patient had imaging done at any time point, captures information about the radiology tests and their findings
Laboratory Results Form	If patient had lab work done at any time point, captures information about the lab tests and their results
Index Visit Treatment Form	Filled out at the index visit only, captures information about randomization and/or cohort designation
Appendectomy Form	If patient had an appendectomy at any time point, captures information about the surgical procedure and treatment decision-making
Pathology Form	If patient had an appendectomy at any time point, captures information about the pathology results
Antibiotics Form	If patient was treated with antibiotics, captures information about the antibiotic treatment (both inpatient and at discharge)
Adverse Events Form	Captures information about adverse events at any time point

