11.3 Protocol Violations and Deviations

A protocol violation is any non-compliance with the clinical trial protocol or Good Clinical Practices. The noncompliance may be either on the part of the participant, the investigator, or the study site staff and most often is related to study enrollment. Anticipated protocol violations are 1) Participant enrolled but did not meet inclusion criteria, 2) Participant enrolled but exclusion criteria present or eligibility criteria not met, 3) Consent not obtained in accordance with IRB guidelines, 4) Randomization failure, 5) Clinical team intervention outside of the protocol (other than those elected by participant), 6) Participant in antibiotics arm received antibiotics outside of protocol during hospital stay, and 7) Participant in antibiotics arm received antibiotics outside of protocol at discharge. Participants enrolled and later found to be ineligible will still be followed. Specifically, a participant enrolled into the randomization or observational cohort that is later found to not have appendicitis will still be asked to complete study assessments. To document the participant's ineligibility, a protocol violation will be submitted. Participants enrolled in the EMR cohort who are later found not to have appendicitis will be withdrawn from the study. As a result of violations, corrective actions will be developed by the site and implemented promptly.

A protocol deviation is a smaller digression from study protocol. Deviations are monitored with consideration for protocol amendment should it become clear that the original protocol was too inflexible. The only anticipated protocol deviations are >7 hours between first administration of antibiotics and study approach by the research coordinator and not watching the video or reviewing the study pamphlet prior to study consent. Additional protocol deviations will be recorded and described.

It is the responsibility of the site to use continuous vigilance to identify and report violations and deviations within 5 working days of identification of the protocol violation/deviation.

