While crossovers are anticipated, the ITT approach is an appropriate primary analysis. We will conduct a secondary as-treated analysis of the primary outcome measure that appropriately accounts for patient- or provider-level characteristics found to be differentially represented among patients who crossover and patients in the antibiotics arm who are treated with appendectomy. Careful as-treated and secondary data analyses are of elevated importance towards understanding the effectiveness of the treatments and in assessing for whom antibiotics-first is an appropriate treatment.⁹ A simple as-treated analysis is problematic because randomization is broken when select patients in the antibiotics and do not undergo appendectomy. Thus, patients who are successfully treated with antibiotics and do not undergo appendectomy may differ demographically or clinically in ways that introduce bias in a naive as-treated analysis. Detry (JAMA 2014) recommends both an ITT and a careful per-protocol analysis to address treatment changes in non-inferiority trials where non-adherence, crossover, or treatment changes are present. If we find a difference between the ITT and as-treated results, the ITT results will be considered the primary analysis.¹⁰

Per-Protocol Analysis: It is important to consider subjects who do not follow the protocol since these individuals bias treatment group comparisons toward no difference, but this is the alternative hypothesis rather than the null hypothesis for non-inferiority trials. Therefore, it is recommended that an ITT analysis is augmented with a per-protocol analysis that considers only those subjects from both treatment groups who adhered to the protocol. Although such a subset analysis may have bias due to patient factors associated

with non-adherence to the protocol it is a valuable companion analysis that does not suffer from nonadherence bias in the way that ITT analysis may. Our protocol states the conditions that are considered to adhere to the protocol, therefore we use the following criteria:

- All patients: exclude not randomized in accordance to the protocol (i.e., meets all inclusion/exclusion criteria, randomization assignment followed)
- Surgical group: exclude subjects whose randomization assignment was ignored.

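### The per-protocol rule does not say when eligibility is judged; if protocol 11.3 is followed, patients who prove not to have appendicitis would probably be dropped mostly from the appendectomy arm

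*SAP*

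**What the plan says.** The final SAP adds a per-protocol analysis because non-adherence pulls an ITT comparison towards no difference, which in a non-inferiority trial is the alternative hypothesis. It introduces the set with "Our protocol states the conditions that are considered to adhere to the protocol, therefore we use the following criteria". The first criterion, for all patients, is "exclude not randomized in accordance to the protocol (i.e., meets all inclusion/exclusion criteria, randomization assignment followed". The resulting mean difference in EQ-5D and its confidence interval are then used to judge non-inferiority in the same way as the ITT result. The SAP warns of bias in this set only from patient factors linked to non-adherence.

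Protocol 4.2 defines the entry diagnosis as "First clinical diagnosis of AUA established by clinical care team, supported by any of the following usual care radiological tests", that is, by what is known at screening.

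Protocol 11.3, on participants who prove ineligible after enrolment, gives this case: "a participant enrolled into the randomization or observational cohort that is later found to not have appendicitis will still be asked to complete study assessments". It continues: "To document the participant's ineligibility, a protocol violation will be submitted".

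Protocol 5.3 describes the pathology form thus: "If patient had an appendectomy at any time point, captures information about the pathology results". For the share of the antibiotics arm likely to have surgery, protocol 2.0 reports that in earlier trials "nearly 3 out of 4 patients in the antibiotics treatment group avoided surgery in the first year after diagnosis".

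**The concern.** Sections 4.2 and 11.3 give different answers for the same patient. Under criterion 2, someone whose appendix later proves normal met the entry requirement. Under 11.3 that person is ineligible. The SAP makes eligibility a condition of the per-protocol set, says that it draws its adherence conditions from the protocol, and does not say which of the two answers applies.

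If the analyst follows 11.3, membership of the set depends on a finding made after randomization, and the chance of making it probably differs by arm. The surgical per-protocol set already leaves out patients whose assignment was ignored, so essentially everyone in it has been operated on and has pathology. In the antibiotics arm only the operated minority does. A patient without appendicitis would then tend to be dropped if randomized to surgery and kept if randomized to antibiotics. This is not the non-adherence bias that the SAP acknowledges.

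At stake is the comparability of the two arms in the analysis meant as a companion check on ITT. The SAP states that analysts know treatment allocation, which is one more reason to fix the rule in writing.

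**Working it through.** The documents state no figure for this effect, so there is none to reproduce. The check is a bias formula with its assumptions shown.

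**Inputs from the documents**
- 1552 patients in equal arms (protocol 8.5 and 8.1): 1552/2 = 776 per arm.
- 90% follow-up at four weeks (8.5): 0.9 × 776 = 698.4 per arm.
- SD 0.12 (8.5); margin 0.05, one-sided alpha 0.025 (8.3 and final SAP).
- Share of the antibiotics arm operated, *s*: about 25% from the year-1 figure in 2.0. The range 10–40% is also shown, since the documents do not say how late a finding may still change the set.

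**Assumed inputs (not in the documents)**
- *q*, the share of randomized patients without appendicitis, equal in both arms by randomization: 1–10%.
- *h*, week-4 EQ-5D of patients without appendicitis minus that of patients with it, the same in both arms: ±0.05 and ±0.10.
- Pathology is the only route of discovery, and operated antibiotics patients have the same *q* as the rest.

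**Step 1: patients dropped.** Appendectomy arm 776*q*; antibiotics arm 776*qs*. The ratio is 1/*s*: 4:1 at *s* = 25%, 10:1 at 10%, 2.5:1 at 40%.

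**Step 2: shift.** All patients without appendicitis leave the appendectomy arm. In the antibiotics arm their remaining share is *r* = *q*(1 − *s*)/(1 − *qs*). The difference (antibiotics minus appendectomy) shifts by *r* × *h*.

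At *s* = 25%:

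| *q* | Dropped, appendectomy | Dropped, antibiotics | *r* | Shift, \|*h*\| = 0.05 (% of margin) | Shift, \|*h*\| = 0.10 (% of margin) |
|---|---|---|---|---|---|
| 1% | 7.8 | 1.9 | 0.0075 | 0.0004 (0.8%) | 0.0008 (1.5%) |
| 3% | 23.3 | 5.8 | 0.0227 | 0.0011 (2.3%) | 0.0023 (4.5%) |
| 5% | 38.8 | 9.7 | 0.0380 | 0.0019 (3.8%) | 0.0038 (7.6%) |
| 10% | 77.6 | 19.4 | 0.0769 | 0.0038 (7.7%) | 0.0077 (15.4%) |

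For the middle case, *r* = 0.05 × 0.75/(1 − 0.0125) = 0.0380, and 0.0380 × 0.05 = 0.0019. Varying *s* from 10% to 40% moves this from 0.0023 to 0.0015.

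**Step 3: against sampling error, middle case.** Analysed numbers are 698.4 × 0.95 = 663.5 and 698.4 × 0.9875 = 689.7. SE = 0.12 × √(1/663.5 + 1/689.7) = 0.0065, and 0.0019/0.0065 = 0.29. At a true difference of −0.05 the chance of declaring non-inferiority is Φ(*rh*/SE − 1.96): 0.048 for *h* = +0.05 and 0.012 for *h* = −0.05, against a nominal 0.025.

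**Step 4: if eligibility is judged only on pre-randomization data.** The same share *q* stays in both arms, and the imbalance is zero in expectation.

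**The case against.** The strongest reply is that the SAP does not remove these patients. Its rule concerns whether a patient was randomized in line with the protocol, and on the wording of criterion 2 a patient with a normal appendix was. The SAP does not cite 11.3 and does not exclude every protocol violation. This stands in part: a reader might infer that the plan definitely drops these patients, and the text does not go that far. But 11.3 calls them ineligible in plain terms, and neither document settles the conflict.

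Second, 11.3 names no source of discovery. That pathology is the main route is an inference from who has a pathology form. Both randomized arms have scheduled record review that includes repeat imaging, so another diagnosis could emerge in either. This also stands, and the 4:1 ratio is therefore illustrative. The true imbalance could also be larger, since antibiotics patients operated on for non-protocol indications leave the set on a separate ground.

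Third, the upper figures are strained. A gap of +0.10 on an expected mean of 0.90 puts patients without appendicitis at the ceiling of 1. At *q* = 5% the same gap gives false non-inferiority rates of 0.084 or 0.006, depending on sign; these should not be read as likely. Mandatory imaging, which protocol 2.1 justifies partly by misclassification in earlier trials, also argues against a rate near 10%.

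Fourth, a reader might extend the point to a neoplasm first seen at histology. The documents do not support that: exclusion 14 is worded as an imaging finding, and the SAP lists neoplasm among its outcomes. Nor would a retained antibiotics patient be scored as a treatment success, because this analysis compares mean EQ-5D and classifies no one.

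**Conclusion.** The point holds as an unresolved conflict between the SAP's eligibility clause, 4.2 and 11.3. One of the available readings produces an exclusion that probably depends on arm. Under the middle assumptions (5% without appendicitis, 25% of the antibiotics arm operated, gap 0.05) the shift is about 0.002 EQ-5D points; the most extreme tabulated case gives about 0.008.

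The direction is unknown. A reader might infer that the exclusion favours antibiotics, but that requires patients without appendicitis to recover better than the rest, and the documents are silent on this. If they recover worse, the shift goes against antibiotics. Nor does the point weaken the trial's main conclusion: ITT remains primary and is untouched. The effect is likely small, but it is systematic where it occurs and wording alone removes it, so the change is worth making.

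**What to change.** In the final SAP's per-protocol criteria, state two things:

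- Inclusion and exclusion criteria are judged in both arms only on data obtained before randomization. This includes a later audit or re-read of those data, so that a true entry error, such as a misread screening scan, can still lead to exclusion.
- Patients found not to have appendicitis from information arising after randomization (pathology, operative findings, later imaging or another diagnosis) stay in the per-protocol set.

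The violation record in protocol 11.3 can remain, provided the SAP says that it does not define the analysis set.

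The cost is a few sentences in the SAP, with no new data or visits. The set will keep some patients without true appendicitis, on the same terms in both arms, which matches the clinically and radiologically diagnosed population that 4.2 enrols.
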